Study	A Phase 1/2, Randomized, Double-Blind, Placebo-Controlled Study to Evaluate the Safety and Efficacy of AstroStem, Autologous Adipose Tissue Derived Mesenchymal Stem Cells, in Patients with Alzheimer's Disease										Protocol
ASP1N2 AstroStem	Date of Assessment DD-MMM-YYYY						Time of Assessment (24-hour clock)				Assessor's Initials
								:			
Visit Number							Subject Number				Subject Initials

Answer for Actual Attempts Only											Most Lethal Attempt Date:
Actual Lethality/Medical Damage: 0. No physical damage or very minor physical damage (e.g., surface scratches). 1. Minor physical damage (e.g., lethargic speech; first-degree burns; mild bleeding; sprains). 2. Moderate physical damage; medical attention needed (e.g., conscious but sleepy; somewhat responsive; second-degree burns; bleeding of major vessel). 3. Moderately severe physical damage; medical hospitalization and likely intensive care required (e.g., comatose with reflexes intact; third-degree burns less than 20% of body; extensive blood loss but can recover; major fractures). 4. Severe physical damage; medical hospitalization with intensive care required (e.g., comatose without reflexes; third-degree burns over 20% of body; extensive blood loss with unstable vital signs; major damage to a vital area). 5. Death											Enter Code _____
Potential Lethality: Only Answer if Actual Lethality = 0 Likely lethality of actual attempt if no medical damage (the following examples, while having no actual medical damage, had potential for very serious lethality: put gun in mouth and pulled the trigger but gun fails to fire so no medical damage; laying on train tracks with oncoming train but pulled away before run over).											Enter Code _____
0 = Behavior not likely to result in injury 1 = Behavior likely to result in injury but not likely to cause death 2 = Behavior likely to result in death despite available medical care											

©2008 Research Foundation for Mental Hygiene, Inc.

Appendix 9. Instruction for Liposuction Procedure

[figure not shown]
Instruction for Liposuction Procedure

1. Pre-procedure for Liposuction

Sterilize operation room with 70% ethanol spray 20-30 min before liposuction procedure.

2. Liposuction Kits (Provided by Biostar, manufacturer)

One kit (plastic bag) includes 20ml-syringes, syringe tip caps, vacuette tubes, labels and sterilization envelopes, as shown in the following:

Syringe 20ml (BD302830)	 
Syringe Tip Cap (BD305819)	 
Vacuette tube (BD367955)	
Sterilization Envelope	
Label	
Label for fat tissues (Syringe) Tissue Samples from Liposuction (AST-ADP2-US01) Subject ID / Initials: Randomization No:
 
Label for fat tissues (sterilization envelope) Tissue Samples from Liposuction (AST-ADP2-US01) Subject ID / Initials: Randomization No: Tissue Collection Date & Time:
 
Label for blood sampling (Vacuette tube) Blood Samples from Liposuction (AST-ADP2-US01) Subject ID / Initials: Randomization No:
 
Label for blood sampling (sterilization envelope) Blood Samples from Liposuction (AST-ADP2-US01) Subject ID / Initials: Randomization No: Blood Collection Date & Time:

3. Preparation for Liposuction

- Saline set, gauze, sterile pad, iodine solution, ring forcep
- 2% lidocaine, No 11 blade
- Tumescent solution (prepare right before the procedure and discard after 1 hour)
 - Hartmann Solution 1L + Lidocaine 1000mg (2% Lidocaine 50ml) + Epinephrine 1mg (= 1mg/ml Epinephrine 1ml)
 - (using 100ml normal saline) normal saline 100ml + Lidocaine 100mg (2% Lidocaine 5ml) + Epinephrine 0.1mg
- 5x Antibiotic-Antimycotic
 - Dilute 100x antibiotic-antimycotic (Thermofisher/Cat NO.15240-096) using sterile saline solution to 5x (sterile saline solution 380ml + 100x antibiotic-antimycotic 20ml) and aliquot 5x antibiotic-antimycotic 400ml into 4ml
 - Freeze aliquots and thaw before use
- 10 cc syringe (Lock syringe; BD 10 ml syringe Luer-Lok Tip; syringe connected to cannula)
- 3-way cock
- Cannula for injection
- Cannula for suction
- 2.5 cc syringe (for anesthesia), 50 cc syringe (for collection of tissues)
- Surgical drape with hole, cotton ball, surgical instrument tray
- Needle Holder, suture (blue nylon 5.0)
- Sharp Scissors
- Towel Clip
- Syringe holder

Figure 1. Liposuction Set-up

4. Cautions for Use

- Before liposuction
 - Stop taking thrombolytic agents such as Aspirin within 5-7 days of liposuction
- After liposuction
 - Your belly be covered in bruises.
 - Your belly may be squeezed.
 - You can take shower, but avoid going and soaking in the bath.
 - You can take pain medicine if necessary.

5. Intraoperative and postoperative monitoring recommendation

Baseline vital signs including blood pressure and heart rate are recorded pre- and postoperatively. Pulse oximeter monitoring is essential in all cases and may be continued after surgery until the patient has fully recovered and is ready for discharge. Although serious complications are rare and any physician

should be able to handle such complications should they arise, it is recommended that a physician trained in resuscitation and emergency care such as a trained anesthetist be available on the premises.

6. Liposuction Procedures

Liposuction procedures can be summarized as three steps: injection of tumescent solution, waiting time, and collection of fat tissues. The detail procedures are instructed below.

- 1) Confirm the subject ID and randomization number before liposuction procedure and write them on each label.
- 2) Collect 60 ml blood (13 of 5 ml Vacuettes serum tubes) before the collection of fat tissues.
- 3) Insert the blood sample bottle into the sterilization envelope and place it in a refrigerator.
- 4) Sterilize skin with iodine solution and cover it with sterile pad.
- 5) Inject small amount (2-3 cc) of 2% Lidocaine, solution for local anesthesia.
- 6) Connect injection cannula, 10 cc lock syringe and solution sets connected to tumescent solution into 3-way cock (Refer to Figure 2).

Figure 2. 3-way Connection

- 7) Make an incision about 2-4mm long with No 11 blade, at around umbilicus (if possible, place where scar is not seen easily).
- 8) Insert slowly the injection cannula into subcutaneous fatty layer (Insert it into right site of belly in case of right-handed subjects).
- 9) Inject the tumescent solution evenly around the liposuction area (Refer to Figure 3).
; the amount of tumescent solution injected is 90-150 cc, which is about 3-5 times of the amount of adipose tissues

Figure 3. Method for using 3-way Stopcock

(Left) Put the solution in the syringe like left figure.

(Right) Inject after spinning 3-way cock like right figure.

- 10) After the injection of tumescent solution, wait for about 15-30 minutes.
- 11) Remove the lock syringe from the 3-way cock and connect to the cannula for suction.
- 12) After the injection of suctioning cannula, collect the adipose tissue by suctioning with about 1~2cm of negative pressure.
- 13) Place the collected adipose tissue into a 50 cc syringe closed with a needle.
- 14) The adipose tissues will float and the tumescent solution will sink to the bottom. Discard the sunken solution and continue the tissue collection until the amount of pure adipose tissue is 30 cc.
- 15) After the sufficient amount of adipose tissues is suctioned, stop the suction.
- 16) Insert 15 cc fat tissues into each 20 ml syringe sealed with tip cap, discard the tip cap, and suck 3ml of 5x antibiotics.
- 17) Close syringe with tip cap, confirm the subject ID and randomization number, insert the syringe into the sterilization envelope, and place it in a refrigerator.
- 18) After completing the fat tissue collection, dress the incision area with #5 blue nylon.
- 19) After completing dressing, inject 1 ampule of lincomycin or gentamycin intramuscularly in order to prevent infection
- 20) Take out stitches after 1 week.

7. Blood Collection Procedures

- 1) Attach corresponding labels to 13 of 5 ml serum tubes.
- 2) Draw 60 ml blood into the tubes.
- 3) Mix gently by inverting the tube eight (8) times. Do not shake.
- 4) Allow blood to clot upright at room temperature for 60 minutes.
- 5) Centrifuge the specimen at room at 3000 rpm, room temperature for 5 minutes

[figure not shown]
8. Transportation Methods of Collected Fat Tissues and Blood

- 1) Prepare 'Adipose Tissue and/or Serum Collection Form'.
- 2) Insert the serum tubes into the sterilization envelope, and place in a refrigerator until the shipment.
- 3) Close syringe with tip cap, attach the label on syringe, insert into the sterilization envelope, and place in a refrigerator until the shipment.
- 4) Insert serum tubes, syringe(s) and the original copy of 'Adipose Tissue and/or Serum Collection Form' into the shipping package provided by the World Courier. (Please find detail instruction on next page)
- 5) Confirm the refrigerated transportation with the World Courier before pick-up.

* *Collected fat tissue and blood shall be delivered to the manufacturing lab as soon as possible. Therefore, please in advance arrange the pick-up of shipping package with the World Courier.*

Shipment of a package with the World Courier

- In advance the pick-up of adipose tissues and/or serum tubes will be arranged with the World Courier.
- At the date when adipose tissues and/or serum tubes are collected the World Courier will bring all materials for packing and shipping the serum tubes.
- The adipose tissues and/or serum tubes and collection form placed in a refrigerator will be inserted into the shipping package provided by the World Courier.

- The product temperature will be monitored using a TempTale 4 Bio Monitor in the package. Temperature should be maintained at (+2 to +8 °C).

- The package will be sent to a manufacturing facility on the same day.

Once the package is arrived to Korea and cleared at the Korea Customs, the World Courier will deliver the package to a manufacturing facility, take back the temperature monitor, and provide shipment temperature record to the sponsor.

Adipose Tissue and/or Serum Collection Form

Prepared by Site (Time zone: PST)

Item	Information	Remarks
Subject ID / Initials	/	
Gender / Age	/	
Randomization No		
Site No / PI Name	Site / Dr.	
Name of Facility		
Date of Collection	(DD/MMM/YYYY)	
Time of Collection	Blood: _____ (HH:MM) Tissue: _____ (HH:MM)	
Volume of Collection	Blood: _____ ml / Tissue: _____ ml	
Collected by	Name: Signature: Date:	
Date and Time of Shipment Pick-up	(DD/MM/YYYY, HH:MM, 24-hr clock)	
Shipment Condition	 Refrigerated	
Tracking No		
Confirmed by	Signature: Date:	

- Please insert the original copy into the shipment package, and please file the photocopy into the ISF binder and send the photocopy to KCRN by email ([contact])

Prepared by Biostar Stem Cell Research Institute (Time zone: KST)

Item	Information	Remarks
Temp. Records from Temp. Monitor	 No excursion  Yes (Please describe excursion in remarks)	
Date and Time of Package Receipt	(DD/MM/YYYY, HH:MM, 24-hr clock)	
Person who Received Package	Name: Signature: Date:	

- Please send the photo copy to KCRN by email ([contact]). KCRN will forward the copy to Site for filing into the ISF binder.

Appendix 10. IP Administration Instruction for Clinical Sites

IP Administration Instructions for Clinical Sites

Only unblinded designee (physician or study coordinator) will open the aluminum bag, dilute IP into saline bags and mask the saline bag and IV tubing with the brown IV bag cover and tubing cover.

Pre-procedure for IP administration

At least 2 hours before the infusion provide 500 mg Aspirin to subjects who are 75 years and older, have had cardiovascular disease, or may need the regimen at investigator's discretion.

Supplies

- Study drug in 20 cc syringe, Qty 2
- 100 cc fluid normal saline, Qty 2
- 18G needle, Qty 2
- Colored standard blood filter tubing set with a 170 to 260 micron filter, Qty 2
- 22G catheter needle, Qty 2
- A labeling with subject information, Qty 4
- Alcohols pads
- Gloves
- IV bag cover, Qty 2

Preparation of IV saline bags with study drug

1. Use aseptic technique when preparing saline bags with the study drug
2. Gather supplies and the study drug
 - Bring out the study drug stored in a refrigerator and open the aluminum foil pack.
 - Confirm the subject ID and randomization number of the study drug.
 - Sign the IP and Label Verification Form once you confirm that the subject ID and randomization number is correct.
 - Only take out one syringe from the aluminum foil pack and bring the pack back to the refrigerator.
 - Confirm all supplies are ready for the procedure.
 - Verify that a subject is not allergic to alcohol. In case a subject has alcohol allergies, alcohol swab can be replaced with 0.2 % Chlorhexidine Gluconate
3. Confirm the subject ID and randomization on the study drug is same with one on the label for a saline bag.
4. Sign the IP and Label Verification Form.
5. Inspect the saline bag. If visibly opaque particles, discoloration, or other foreign particulates are observed, the bag should not be used.

6. Attach the label on the top of the saline bag.
7. Confirm the subject ID and randomization of the study drug is the same with the label attached to the saline bag.

8. Gently invert syringes 15-20 times. Do not mix vigorously or vortex.
9. Connect 18G needle to a 20cc syringe.
10. Disinfect the saline bag access port with alcohol swab.
11. Insert needle and inject the contents into a saline bag with rate of 1 cc /20-25 secs.

12. After injection, mix the saline bag gently. Don't shake the bag.
13. Cover the IV bag with the brown IV bag cover in order to maintain the blind to other study staffs and subjects prior to sending dose to be infused
14. Attach the label on the top of the brown IV bag cover and confirm the subject ID and randomization of the study drug is the same with the label attached to the IV bag cover.

15. The study drug infusion should begin within 20 minutes of mixing.

Infusion Procedures

1. Use aseptic technique when preparing and administering fluids and medications

2. Insert the spike of the colored IV tubing into the saline bag mixed with the study drug.
3. Select a vein that is well-dilated. The selection priority of vein will be the following; Dorsal venous plexus, metacarpal plexus, basilica vein, cephalic vein, median cubital vein.
4. Perform the venipuncture.
5. Hang the saline bag on an IV pole.
6. Adjust to the desired flow rate. The infusion time for one saline bag is 1-3 hours. The infusion rate will be determined by PI's discretion but maximum infusion rate will be 25 gtt/min (100cc/ hr).
7. Gently squeeze the saline bag every 30 min to prevent cell settling.
8. Document the relevant data regarding infusion.
 - Record the start time of the infusion on the client's chart.
 - Include the date and time of the venipuncture
 - Specific name and location of the accessed vein
 - Flow rate
 - Type, length and gauge of the needle or catheter
 - The client's general response
 - Your signature
9. Another saline bag should be mixed with the study drug stored in the refrigerator before the infusion of the first saline bag is finished. Follow the same procedure to prepare the second saline bag.
10. Once the infusion of the first saline bag is finished, close the roller clamp.

11. Take out the spike of the colored IV tubing from the first saline bag and insert into the second saline bag mixed with the study drug.
12. Hang the saline bag on an IV pole.
13. Adjust to the desired flow rate again. The infusion time for one saline bag is 1-3 hours. The infusion rate will be determined by PI's discretion but maximum infusion rate will be 25 gtt/min (100cc/hr).
14. Gently squeeze the saline bag every 30 min to prevent cell settling.
15. Document the relevant data regarding infusion.
 - Record the start time of the infusion on the client's chart.
 - Include the date and time of the venipuncture
 - Specific name and location of the accessed vein
 - Flow rate
 - Type, length and gauge of the needle or catheter
 - The client's general response
 - Your signature
16. Once the infusion of the second saline bag is finished, perform saline flush with approximate 20 cc of saline to make sure entire IP is administered.
17. Once the saline flush is finished, close the flow regulator of IV tubing. Apply gentle pressure over the insertion site with sterile gauze. Withdraw the needle. Hold pressure on the insertion site until bleeding stops. Cover the insertion site with an adhesive bandage.
18. Enclose empty two syringes of study drug and two IV bags into a pre-labeled bag and seal with tamper tale. Store at the secure place until a close-out visit.
19. A subject should stay in the infusion bed/chair at least 1 hour after infusion.
20. A subject will be discharged by PI's discharge order.

Monitoring Plan during and after the IV infusion of the study drug

1. Document the relevant data regarding infusion.
 - Record the start time of the infusion on the client's chart.
 - Include the date and time of the venipuncture
 - Specific name and location of the accessed vein
 - Flow rate
 - Type, length and gauge of the needle or catheter
 - The client's general response
 - Your signature
2. Check tubing for anything that might interfere with flow. Be sure clamps are in the open position.

3. Inspect the site for swelling, leakage at the site, coolness, or pallor, which may indicate infiltration. Ask if subject is experiencing any pain or discomfort. If any of these symptoms are present, the IV will need to be removed and restarted at another site.
4. Inspect the site for redness, swelling, and heat. Ask if patient is experiencing pain. The findings may indicate phlebitis. Notify principle investigator (PI) if phlebitis is suspected. IV will need to be discontinued and restarted at another site.
5. Check for local manifestations (redness, pus, warmth, induration, and pain) that may indicate an infection is present at the site or systemic manifestations (chills, fever, tachycardia, and hypotension) that may accompany local infection at the site. If signs of infection are present, discontinue the IV and notify PI.
6. If subject is experiencing shortness of breath and chest pain, discontinue the IV and notify PI. With PI's discretion, IV infusion will be terminated.

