3.2.2 Exclusion Criteria

- 1) Subjects who are female who are pregnant, nursing, or childbearing potential while not practicing effective contraception
- 2) Subjects who have signs of delirium
- 3) Subjects who have had cortical stroke within the preceding 2 years
- 4) Subjects who have a prolonged QTc interval; >450 msec in male or >470 msec in female at screening
- 5) Subjects who have diagnosis of severe white matter hyperintensity (WMH), which is defined as $\geq 25\text{mm}$ of the deep white matter and $\geq 10\text{mm}$ of the periventricular capping/banding in lengths
- 6) Subjects who have diagnosis of dementia or cause of cognitive impairment other than Alzheimer's disease
- 7) Subjects who have a significant abnormal result in laboratory tests, in the opinion of the investigator
- 8) Subjects who have participated in any investigational drug, stem cell therapy, or device trial within the previous 3 months at screening
- 9) Subjects with any current psychiatric diagnosis other than AD if, in the judgment of the investigator, the psychiatric disorder or symptom is likely to confound interpretation of drug effect, affect cognitive assessments, or affect the subject's ability to complete the study
- 10) Subjects who are known to have autosomal dominant mutation-associated presenile AD
- 11) Subjects who show signs of AIDS (Acquired Immunodeficiency Syndrome), HBV (Hepatitis B Virus), HCV (Hepatitis C), VDRL (Venereal Disease Research Laboratory)
- 12) Subjects who have any conditions that would contraindicate an MRI, such as the presence of metallic objects in the eyes, skin, or heart
- 13) Subjects who have > 4 cerebral microhemorrhages (regardless of their anatomical location or diagnostic characterization as "possible" or "definite"), a single area of superficial siderosis, or evidence of a prior microhemorrhage as assessed by MRI

- 14) Subjects who have history of malignant cancer within the last 5 years (The following is a partial list of conditions that are permissible for study entry: non-metastatic basal and/or squamous cell carcinoma of the skin, in situ cervical, or non-progressive prostate cancer)
- 15) Subjects who have suspected active lung disease based on chest X-ray
- 16) Subjects who are hypersensitive to fetal bovine serum or penicillin

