- 17) Subjects who are currently using immunosuppressants, cytotoxic drug, corticosteroids or similar steroid anti-inflammatory medication (e.g., Prednisone) on a regular basis (exceptions allowed include; regular use of steroid nasal sprays, topical steroids, and estrogen-replacement therapy)
- 18) Subjects for whom the investigator judges the liposuction can cause any problems
- 19) Subjects who have history of local anesthetic allergy

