3.3 Removal of Subjects from Study

Subjects may be withdrawn from the study for the following reasons:

- At their own request or at the request of their legally acceptable representative
- If, in the investigator's opinion, continuation in the study would be detrimental to the subject's well-being
- At the specific request of the sponsor

Also, subjects must be withdrawn for the following reasons:

- A significant violation of the protocol, as determined by the sponsor or the investigator
- Highly significant abnormalities in the laboratory results (Highly significant abnormalities generally follow lab related exclusion criteria, but a PI can determine the high significance on any abnormalities for the safety of subject)
- Use of any other investigational drugs
- Subjects enrolled in the current trial but taking any prohibited medication/therapy stated in the inclusion/exclusion criteria
- Subject enrolled in the current trial but having a baby

If a subject prematurely withdraws from the study, the subject must return to the clinical site for the early termination visit. In all cases, the reason for withdrawal must be recorded in the electronic Case Report Form (eCRF) and in the subject's medical records.

Contact will be maintained with subjects who are removed due to an adverse event (AE) until it has been resolved or stabilized, and the information will be documented in the eCRF and in the subject's medical records.

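### Appendix 10 directs 500 mg aspirin before infusion for two groups of subjects, with no instruction to withhold it for a contraindication or after a new cerebral microhemorrhage

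*Protocol*

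**What the plan says.** The aspirin instruction stands near the top of Protocol Appendix 10, ahead of the list of supplies: "At least 2 hours before the infusion provide 500 mg Aspirin to subjects who are 75 years and older, have had cardiovascular disease". A third category adds anyone the investigator thinks may need it. For the two named groups the instruction is unconditional; the discretion only adds subjects.

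Both groups can enroll. Section 3.2.1 sets a minimum age of 50 and no maximum. Section 3.2.2 does not exclude cardiovascular disease in general; the nearest items are a recent cortical stroke and a prolonged QTc.

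The protocol names specific sensitivities elsewhere:

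- Exclusion 16: "Subjects who are hypersensitive to fetal bovine serum or penicillin".
- Exclusion 19: "Subjects who have history of local anesthetic allergy".
- Appendix 10, before swabbing: "Verify that a subject is not allergic to alcohol".

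On bleeding and brain lesions:

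- Appendix 9, cautions before liposuction: "Stop taking thrombolytic agents such as Aspirin within 5-7 days of liposuction".
- Exclusion 13 lists more than 4 microhemorrhages, superficial siderosis, or "evidence of a prior microhemorrhage as assessed by MRI".
- Section 7.4 answers a new asymptomatic microhemorrhage with close follow-up and a repeat MRI of unspecified date. It does not mention aspirin or holding an infusion, and it gives no separate action for a symptomatic microhemorrhage.
- The check before each repeat infusion (Sections 4.2.2 to 4.2.6) covers only infusion-type, allergic or anaphylactic reactions to the preceding study-drug dose.

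**The concern.** The protocol itself orders an antiplatelet drug for older subjects and those with cardiovascular history, in a trial that monitors the brain for microhemorrhage. It asks about alcohol allergy before a skin swab but not about aspirin intolerance before 500 mg of aspirin. It takes subjects off aspirin for liposuction but has no matching rule once it prescribes aspirin itself.

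A site that followed the text exactly would give aspirin to a subject in a named group who has aspirin/NSAID intolerance, has a bleeding disorder or takes an anticoagulant (anticoagulants are not on the Section 3.5.7 prohibited list). It would also go on giving aspirin after a new lesion was seen at Week 12. What is at stake is the safety of individual subjects.

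**Working it through.** **Number of directed doses.** Section 3.5.1 gives one infusion at each of Visits 3 to 12: 12 − 3 + 1 = 10. The synopsis agrees: the Week 0 infusion is repeated 9 times (1 + 9 = 10), and Week 18 is listed as the 10th. At 500 mg each:

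- Aspirin before every infusion: 10 × 500 mg = 5,000 mg = 5 g.
- Aspirin before the first infusion only: 1 × 500 mg = 0.5 g.

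The first reading is the likelier. Appendix 10 is the general administration instruction, the same infusion recurs at Visits 4 to 12, and no text limits aspirin to one dose. It remains a reading, because Appendix 10 refers to the infusion in the singular and only Section 4.2.1 (Visit 3) cites the appendix.

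**Doses after a new lesion.** Section 7.4 schedules MRI at screening, Week 12 (Visit 9), Week 30 and Week 52. Only the Week 12 scan falls within the dosing period, and it shares a visit with the 7th infusion. Section 4.2.5 does not fix the order of scan, reading and infusion.

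| Scan read | Visits still to be dosed | Aspirin still directed | Share of 5 g |
|---|---|---|---|
| After the Visit 9 dose | 10, 11, 12 (3 doses) | 3 × 500 mg = 1.5 g | 1.5/5 = 30% |
| Before the Visit 9 dose | 9, 10, 11, 12 (4 doses) | 4 × 500 mg = 2 g | 2/5 = 40% |

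The next scheduled scan comes 30 − 12 = 18 weeks after the Week 12 scan, and 30 − 18 = 12 weeks after the last infusion. Because 7.4 gives no date for the extra follow-up MRI, all remaining doses can precede it.

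**Do the other provisions close the gap?**

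| Provision | What it does | Tied to the aspirin? |
|---|---|---|
| Medical and medication history at Visit 1; medication changes at later visits | Collects the relevant information | No |
| Exclusion 7: "Subjects who have a significant abnormal result in laboratory tests, in the opinion of the investigator" | Screens at entry; the Appendix 1 panel includes platelets and PT-INR | No |
| Exclusion 18 (liposuction judged likely to cause problems) | Can remove subjects at bleeding risk at entry | No |
| Platelets and PT-INR again at Visits 3, 6, 9 and 12; Section 3.3 mandatory withdrawal for highly significant laboratory abnormalities | Controls participation on treatment | No; it does not cover MRI findings |
| Section 3.3, withdrawal when "continuation in the study would be detrimental" | Optional removal from the study | No |
| Section 3.5.7, reassessment when a concomitant medication is given | Decides continued participation | No |
| Section 5.2, deviation to remove an immediate hazard | Permits departing from the protocol, with explanation and documentation | No; it permits withholding but does not direct it |

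Each provision supplies information, governs entry or participation, or permits a departure. None tells the site when not to give the aspirin.

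**The case against.** The strongest reply is that the investigator already has the information and the authority. Anticoagulant use is visible in the medication record, exclusion 18 is a natural route for screening out a bleeding disorder, coagulation tests are repeated on treatment, and Section 5.2 lets the investigator act on an immediate hazard without prior approval. This stands as far as it goes: it would be wrong to say that subjects have no protection. But for someone in a named group, withholding aspirin remains a departure from the written instruction, to be justified afterwards, when it should be the instruction itself.

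A second reply is that the documents nowhere link aspirin to MRI findings; the liposuction caution concerns a different procedure. That also stands. The microhemorrhage part rests on ordinary clinical judgment about an antiplatelet drug, so the hold should be one that the investigator can override with a documented reason.

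Four stronger readings might be inferred, and the documents do not support them:

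- *Entry is strict on microhemorrhage and treatment is lax.* Exclusion 13 is ambiguous: a limit of more than 4 would be redundant if any prior lesion excluded, so subjects with 1 to 4 might enroll. The contrast cannot be treated as settled.
- *Every subject gets aspirin 10 times.* It is directed for two groups and discretionary for the rest, and repetition at each infusion is an inference.
- *The primary safety endpoint is biased.* The fixed criteria apply alike to both arms, and AEs are collected at every visit.
- *The Section 7.3 SAE start is an aspirin problem, because the first dose precedes the first study-drug administration.* That concerns a short interval around one dose. The same start rule leaves the period from liposuction, four weeks earlier, outside SAE reporting, so it is a separate and wider matter.

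**Conclusion.** The gap is real and specific. Appendix 10 directs aspirin for two groups with no check for intolerance, bleeding disorder or anticoagulant use, and nothing in Section 7.4 or the re-dosing check stops it after a new microhemorrhage. The size is a dose count: up to 5 g per subject in a named group, with 1.5 to 2 g still directed after a Week 12 lesion. Those figures assume aspirin before every infusion and a subject who receives all ten. If aspirin were meant for the first infusion only, the post-lesion exposure disappears, but the missing contraindication check remains at that dose.

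The documents do not say how many subjects fall in the named groups or would have a contraindication, so no event rate can be given. No analysis or sample-size figure is affected.

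**What to change.** Add to Appendix 10, with a cross-reference in Section 7.4:

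*Before each dose, check for aspirin/NSAID intolerance, bleeding disorder and anticoagulant use. Do not give the protocol-directed aspirin if any is present, or after a new microhemorrhage on MRI unless the investigator documents why benefit outweighs risk. The investigator records whether infusions continue without it.*

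The opening words also settle whether the instruction applies to every infusion.

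The cost is a short amendment and no change to the analyses. The downside is that some subjects in the named groups would be infused without aspirin or would miss infusions. The protocol gives no reason for the aspirin, so the investigator has no stated basis for weighing that loss; a line giving the sponsor's rationale would help.
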